8.0 LABORATORY SPECIMENS

This study will adhere to standards of good clinical laboratory practice and local standard operating procedures for specimen management, including proper collection, processing, labeling, transport, and storage of specimens.

8.1 Laboratory Specimens

As described previously, the following types of specimens will be collected for laboratory testing throughout this study for those **who initiate PrEP**:

Blood Specimen: To be used for **HIV testing**, confirmatory HIV testing, **syphilis** rapid plasma reagin (RPR), serum **creatinine**, **Hepatitis B** Surface Antigen (HBsAg), dried blood spot (DBS) for measuring tenofovir diphosphate (TVF-DP) levels in plasma for PrEP adherence measure.

Dried Blood Spot: Participants who initiate PrEP will be asked at an interim visit for permission to collect blood to create a dried blood spot (DBS) for research purposes. Participants have consented to this procedure, from the consent form, "An additional blood sample may also be collected to determine how much of the PREP drug, Truvada, is present in your blood." An additional short questionnaire, contained from currently IRB-approved survey Section B: Sexual History and Section E: PrEP Intention, will be asked for the most recent information prior to blood collection. For this additional participation, we will provide an extra 300RMB (\$45) incentive.

Urine Specimen: To be used for urethral chlamydia and gonorrhea testing

Rectal Swab Specimen: To be used for rectal chlamydia and gonorrhea testing

Pharyngeal Swab Specimen: To be used for pharyngeal chlamydia and gonorrhea testing

9.0 SAFETY MONITORING AND ADVERSE EVENT REPORTING

Research staff will establish a data and safety monitoring plan. The PIs and project coordinators in China and in Atlanta will monitor data collection throughout the study. They will ensure that interview protocols are followed, review all adverse event reports (if any), and ensure that confidentiality procedures are implemented. The larger project team will meet regularly via telephone to discuss progress toward study goals and objectives. At these meetings, research staff will prepare reports on data collection and any emerging issues or potential problems regarding data collection efforts. The following will be reported by site PIs in writing: all serious adverse events associated with the study procedures and/or any incidents or problems involving the conduct of the study staff or subject participation, including problems with the consent process.

9.1 Data Management, Analysis, and Quality Assurance Plan

Data sources for the intervention will include electronic surveys, case report forms tracking participant engagement in PrEP care, app paradata, and biological specimens. All data will be stored electronically, with 256-bit SSL encryption and under password protection. Further, role-based access will be implemented to limit access to sensitive data. Study staff will each have their own log-in to the electronic data platform, and will only have access to data needed to perform their study role. Back-up servers are used by all electronic study platforms. Emory will on a regular basis download all study data, and back-up these data on secure Emory servers. High levels of data quality will be assured through numerous data validation checks and post-check procedures, implemented throughout all study data collection areas. Additionally, the study data manager will create weekly reports on the progress of the study, including key areas of reporting such as accrual of participants by site, laboratory results and processing through the intervention system by site, and participant fall-off charts to facilitate retention in study processes. This weekly reporting is a procedure Drs. [name] and [name] have employed to ensure high data quality and attainment of study benchmarks in terms of recruitment and retention. The data manager will also be tasked, in collaboration with study investigators, of ensuring data quality compliance that will allow for reporting consistent with Good Clinical Practice guidelines. Given that this is a pilot feasibility study, no DSMB will be used.

9.2 Specification of Safety Parameters

9.2.1 Adverse Events

An adverse event (AE) is defined as any untoward medical occurrence in a clinical research participant administered an investigational product or intervention. In this study, the study product or interventions include the HIV prevention interventions, including the study app and PrEP. Possible adverse events for study participants may include:

1. Participant report of loss of confidentiality through the app or its functions
2. Participant report of loss of confidentiality through delivery of prevention supplies or commodities
3. Participant report of access by others to protected health information through the app or study procedures

4. Participant report of disclosure of status as a research participant due to study-related reminders (from app, phone calls, emails, or text messages)
5. Participant report of discomfort or injury due to use of provided specimen collection materials
6. Disclosure of personal information about health, sexuality, or sexual practices that results in physical violence or threat of violence
7. Disclosure of personal information about health, sexuality, or sexual practices that results in adverse effects on employment

9.2.2 Serious Adverse Events

1. Suicidal behavior or intention, including but not limited to following learning the results of study-provided tests (e.g., HIV tests)
2. Any event that results in death, is life-threatening, results in persistent or significant disability/incapacity, or requires hospitalization or prolongation of existing hospitalization

9.2.3 Relationship to study intervention

The potential event relationship to the study intervention and/or participation is assessed by the site investigator. A comprehensive scale in common use to categorize an event is:

- *Definitely Related*: The adverse event is clearly related to the investigational intervention – i.e. an event that follows a reasonable temporal sequence from first exposure to the app, follows as a known or expected consequence from using the intervention, and that could not be reasonably explained by the known characteristics of the subject's normal activities.
- *Possibly Related*: An adverse event that follows a reasonable temporal sequence from exposure to the app, follows a known or expected consequence from use of the app, but that also could readily have been produced by a number of other factors.
- *Not Related*: The adverse event is clearly not related to use of the app – i.e. another cause of the event is most plausible; and/or a plausible temporal sequence is inconsistent with the onset of the event and the study intervention and/or a causal relationship is considered implausible.

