Study Design:

The pilot study will be an interrupted time series cohort of 400 MSM. In two cities, a three-month baseline standard of care (SOC) period with measurement at 0 and 3 months will be followed by a 12-month intervention period with the measurement at 6, 9, 12, and 15 months. The longitudinal design will allow for 1) assessment of feasibility and acceptability outcomes, 2) development of the logistical and operational needs to provide the app-based intervention, and 3) development of estimates for key parameters to design a future, definitive study to determine intervention efficacy.

Standard of care will consist of the existing Blued app and local health services. Blued app access currently includes health education components such as information regarding HIV testing and pre-recorded health messages from Chinese celebrities. Participants will have access to in-person no-cost services for HIV testing and condom pick-up from local non-governmental organizations (NGOs) that support MSM in both cities.

At three months, participants will be provided with educational materials in the health portal as well as theory-based HIV prevention messages, along with home HIV test kits and condoms. This intervention will have a health portal that houses all HIV prevention functionalities. The exact nature of the interventions included will be further defined by the qualitative work, as additional services may be identified as essential to an HIV prevention package in China. These may include services such as peer support or stigma reduction. Additionally, participants will receive PrEP medication, laboratory, and care costs free of charge.

In the portal, users will be able to explore health-supporting functions of the app and access offline services, including behavioral risk assessments, an HIV prevention platform, HIV testing, linkage to care for those testing positive for HIV, in-app screening and referral to HIV pre-exposure prophylaxis (PrEP) and sexually transmitted infection (STI) services, and provision of PrEP with emtricitabine/tenofovir disoproxil fumarate (FTC/TDF).

Study Population:

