5.4.5.2 Discontinuation of PrEP in the Presence of Toxicity

Grades 1 or 2

In general, participants who develop a Grade 1 or 2 AE regardless of relatedness to study drug and that is not specifically addressed below, may continue use of the study drug per protocol.

Grade 3

For participants who develop a Grade 3 AE or toxicity that is not specifically addressed below and is judged to be related to study drug by the study investigator, study drug use should be temporarily discontinued. In general, the investigator should re-evaluate the participant at least weekly for up to 2 weeks to document resolution of toxicity to less than Grade 2. The study drug should be permanently discontinued if improvement to severity \leq Grade 2 cannot be documented within four weeks of receipt of the initial results.

Grade 4

Participants who develop a Grade 4 AE or toxicity that is not specifically addressed below (regardless of relationship to study drug) should have the study drug temporarily discontinued. The investigator should consult with the Protocol Safety Review Team (PSRT) and continue the temporary study drug hold until a recommendation is obtained from the PSRT. In general, study drug use will not be resumed if the Grade 4 AE is considered related to study drug use. If, in consultation with the PSRT, study drug use is resumed and the same Grade 4 AE recurs at Grade 4 level at any time, study drug must then be permanently discontinued.

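### The relatedness categories in 9.2.3 revert to the app, so a possible FTC/TDF reaction can be recorded as Not Related

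*Combined protocol and SAP*

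**What the plan says.** Section 9.2.1 sets the scope for adverse events: "the study product or interventions include the HIV prevention interventions, including the study app and PrEP". Section 9.2.3 opens with the same breadth: "The potential event relationship to the study intervention and/or participation is assessed by the site investigator".

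The three category definitions that follow are narrower:

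- *Definitely Related* begins with the intervention, but its timing criterion is "an event that follows a reasonable temporal sequence from first exposure to the app". Its consequence criterion returns to the intervention.
- *Possibly Related* is an event that "follows a reasonable temporal sequence from exposure to the app, follows a known or expected consequence from use of the app", where other factors could readily have produced it too.
- *Not Related* opens with "The adverse event is clearly not related to use of the app" and is explained by alternatives joined by and/or: another cause is most plausible, the timing is "inconsistent with the onset of the event and the study intervention", or a causal link is implausible.

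Drug toxicity is handled separately in 5.4.5 and 5.4.6. For a Grade 3 event not otherwise addressed, 5.4.5.2 says that if it "is judged to be related to study drug by the study investigator, study drug use should be temporarily discontinued". That judgement is made directly against the drug and does not cite 9.2.3.

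**The concern.** FTC/TDF is the component of the package most likely to cause a medical adverse event. Section 11.3.2 lists gastrointestinal effects, allergic reactions, bone pain, mood changes, and kidney and liver symptoms. None of these is an expected result of using a phone app. The middle category of a causality scale is where uncertain drug reactions normally belong, and here it is the one category worded for the app alone.

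At stake is the causality record for the drug. Possible reactions could be filed as unrelated, or two site investigators could label the same event differently according to how broadly each reads the app. Section 1.0 says that data on the feasibility of providing PrEP will matter for eventual approval in China, so a clean record has some value even in a pilot.

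**Working it through.** The point concerns wording, so the check is to list each clause in 9.2.3 that names an exposure and then run a test case through the scale.

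**Step 1. Exposure named by each clause**

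| Category | Clause | Exposure named |
|---|---|---|
| Definitely Related | opening | intervention |
| Definitely Related | timing | app |
| Definitely Related | consequence | intervention |
| Possibly Related | timing | app |
| Possibly Related | consequence | app |
| Not Related | opening | app |
| Not Related | timing | intervention |

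App: 1 + 2 + 1 = 4 of 7. Intervention: 2 + 0 + 1 = 3 of 7. PrEP, FTC/TDF or study drug: 0 of 7. All three categories contain an app criterion; one of the three, *Possibly Related*, is app-only.

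**Step 2. Test case.** Take a participant on FTC/TDF with non-serious nausea that the drug may have caused but that has other plausible explanations.

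- *Definitely Related*: not met, because the event is not clearly due to the intervention.
- *Possibly Related*: both criteria must hold. Nausea is not a known or expected consequence of using an app, so the second fails.
- *Not Related*: the opening can be met, because nausea is clearly not due to the app. The first explanatory alternative can be met too, because something other than the app is the most plausible cause. The clause that mentions the study intervention is an and/or alternative, so it need not be satisfied.

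An investigator who follows the words can therefore arrive at *Not Related*.

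**Step 3. What uses the label**

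| Decision or output | Depends on the 9.2.3 label? |
|---|---|
| Grade 3 hold and Grade 4 restart (5.4.5.2) | No: separate judgement of relatedness to study drug |
| Grade 4 hold (5.4.5.2) | No: applies whatever the relationship |
| Gastrointestinal, creatinine and HIV rules (5.4.6) | No: own criteria |
| Hold or discontinuation at discretion (5.4.5, 5.4.5.3) | No |
| Expedited reporting of serious events (9.3.1) | No: covers all of them |
| Feasibility and acceptability benchmarks (6.0, 10.1) | No |
| Planned analyses (10.3, 10.4) | No: none uses relatedness |

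**Step 4. Scale.** If the PrEP benchmark is just met, the men with a prescription number 400 × 0.15 = 60 (benchmark in 10.1) to 400 × 0.20 = 80 (benchmark in the 6.0 table). This counts men for whom drug relatedness could arise. It is not a count of misclassified events, which cannot be estimated because no adverse event rate is given.

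**The case against.** The best defence is that the app stands for the whole package. Section 2.1 describes Blued+ as prevention services integrated into the app platform, and 5.3.1 lists provision of PrEP among its core components. On that reading a drug reaction is a consequence of using the app. This shows that the text is ambiguous, so it would go too far to say that no reading lets an FTC/TDF event be *Possibly Related*. But the reading is strained, because 9.2.1 lists the app and PrEP as separate items.

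A second defence is that section 9.2 was written mainly for social harms. None of its seven example events is an FTC/TDF side effect, and the severity definitions in 9.2.4 refer to social harms and specimen-collection injury. Drug toxicity has its own grading and rules in 5.4.5 and 5.4.6. This explains the wording and limits the harm, but 9.2.1 still places PrEP within the scope of the scale. Third, the heading and lead-in of 9.2.3 make the intended scope clear. That is a good reason to bring the definitions into line with it.

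A reader might infer more than the documents support:

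- *That drug holds or serious-event reporting are compromised.* They do not use this label.
- *That the app is a seriously wrong clock.* The schema has the baseline period "followed by a 12-month intervention period with the measurement at 6, 9, 12, and 15 months", so a first dose could in principle come up to 15 − 3 = 12 months after the portal opens. That is the extreme case. No time window is stated, and only *Definitely Related* counts from first exposure.
- *That 5.4.5.2 is defective for not saying whether possibly related counts as related.* It does not rely on 9.2.3, and the choice is a clinical-policy trade-off.
- *That 9.0 and 9.3.1 conflict over which serious events are reported.* They can be read as duties of different reporters.

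**Conclusion.** The point holds as a drafting error of low severity. The definitions in 9.2.3 contradict the scope set in 9.2.1 and in their own lead-in. Applied as written, they allow a non-serious event possibly caused by FTC/TDF to be recorded as *Not Related*. The effect stops at the recorded causality of FTC/TDF events. The same label could be put on a serious event, but its expedited reporting would go ahead regardless.

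This rests on two assumptions: that investigators apply the category wording rather than the lead-in, and that no other document settles the matter. The clinician-completed PrEP case report forms (7.4) and the planned data and safety monitoring plan (9.0) are not in the file and may already record drug relatedness.

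**What to change.** In 9.2.3, replace the app in all four places with *the study intervention (app, study procedures or FTC/TDF)*, and state that timing is taken from exposure to the component concerned. Record relatedness to FTC/TDF separately, with the same three categories, if the PrEP case report form does not already do so. If the data and safety monitoring plan covers this, cite it in 9.2.3.

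As a separate minor correction, 12.2 sends protocol violations to a DSMB, while 9.1 says none will be used. Name a body that exists, such as the IRBs alone or the Protocol Safety Review Team of 5.4.5.2.

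The cost is four wording replacements, one phrase on timing, at most one form field and one correction in 12.2. Sample size, visit schedule, benchmarks and drug-hold rules are unchanged.

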9.2.4 Severity of Event

Severity will be classified using the following standards:

- *Mild*: Awareness of the issue, but easily tolerated and are of minor irritant type causing no loss of time from normal activities. Incident did not require counseling or a medical evaluation; concern on the part of the participant or physical symptoms were transient.
- *Moderate*: Events introduce a low level of inconvenience or concern to the participant and may interfere with daily activities, but are usually improved within a few days (social harms) or by simple therapeutic measures (injury due to specimen collection); moderate experiences may cause some interference with usual activities for a few days.

- *Severe*: Events interrupt the participant's normal daily activities and require mental health assessment and treatment (social harms) or clinical treatment (injury due to specimen collection); they usually produce major disruptions in daily activities such as work, school, or family commitments.

9.3 Reporting Procedures

In all study sites, new confirmed STI infections, including HIV, are reportable to local health departments. We will complete mandatory notification of positive STI results as required by law. Participants will be informed in the informed consent process and counseled when receiving positive STI results that results will be reported to the health department as required by law, and that the health department might contact them to offer treatment or to assess possible onward exposures. Abuse that comes to the attention of study staff will be required to be reported in all jurisdictions if the abuse is perpetrated on a child (who would be ineligible to participate per the study age criteria), or if the abused person is a vulnerable adult (e.g., elderly person, person in a long-term care facility). We do not anticipate having participants who would be considered to be vulnerable, but if we become aware of abuse to a person meeting this criterion, we will report to authorities as required by law.

9.3.1 Serious Adverse Event Reporting

All serious adverse events (SAEs) require expedited reporting by the Principal Investigator to the Emory IRB. An expedited report of an SAE can be submitted by telephone, fax, or email and must be reported to the IRB and the NIH project officer within 24 hours of the event being reported to the investigator.

The expedited report will be followed by a detailed, written SAE report of the event and its resolution as soon as possible but no longer than 72 hours after the study team learns of the event. Follow up information may be required and asked for by the IRB directly, or through the NIH or its representative. A standardized SAE reporting form will be used.

10.0 STATISTICAL/ANALYTIC CONSIDERATIONS

10.1 Primary Outcome

As called for by the MP3 mechanism, the primary analysis assesses the feasibility and acceptability of the pilot intervention as opposed to efficacy. This will be assessed based on a series of benchmarks. The intervention will be determined to be feasible if a minimum proportion of participants receive services for home HIV testing (benchmark $\geq 30\%$), and PrEP prescription (benchmark $\geq 15\%$). Benchmark targets were determined based on modeling in other contexts that indicates minimum levels of service uptake to substantially influence an HIV epidemic. The intervention will be considered acceptable if it reaches a systems usability scale rating benchmark score of 'good' (≥ 71 out of 100) and Likert component mean rating benchmark of 'acceptable' (≥ 3 out of 5).

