The study population will be self-reported HIV-negative Blued users who are 18 years of age or greater, were assigned a male sex at birth, report having anal sex with a man in the last 6 months, are able to complete a survey in standard Mandarin Chinese, are willing to provide two forms of contact information, are willing to update the Blued app with the Blued+ portal after the baseline period, are willing to complete quarterly surveys for the 15-month study period, and reside in metropolitan Beijing or Chengdu, China.

Study Size:

The sample for the pilot study will consist of approximately 400 MSM, 200 each in Beijing and Chengdu. All 400 men will be followed for 15 months.

Study Duration:

Recruitment activities will be conducted for three months or until 200 MSM have been recruited in each intervention city. After enrollment, MSM will have a follow-up period of 15 months for each participant.

Primary Objectives:

This study has four primary objectives:

1. Conduct a review of literature on behavioral and biomedical interventions offered in online and offline settings for MSM in China.
2. Develop a mathematical model of HIV transmission in Chinese MSM, informed by annual cross-sectional surveys, that accounts for behavioral, structural, and biological factors in order to estimate the impact of different scenarios of intervention provision and inform selection of intervention components for the pilot study.
3. Assess Blued+ intervention feasibility and acceptability in China, first by collecting qualitative data to inform the development of the Blued+ app components and service delivery and then by developing and pilot testing Blued+ among MSM in Beijing and Chengdu, China. This protocol includes only the pilot study portion of the overall study.
4. Use preliminary information from the pilot study to design a larger, definitive study of the efficacy of the prevention package for Chinese MSM.

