6.0 MEASURES

A summary table of study measures, and sources for each measure, are provided in the table below. Measurement of tenofovir-diphosphate (TFV-DP) levels will be conducted using liquid chromatography/tandem mass spectrometry methods on DBS samples. TFV-DP level can be translated to an interpretation that indicates mean number of days per week PrEP is ingested over a period of approximately one month. The cutpoint used will be TFV-DP levels considered a surrogate for substantial protection: >700 fmol/punch, a level indicating >4 doses/wk.

Construct	Measure	Data source	Definition	Analysis
PRIMARY OUTCOMES				
Feasibility	Home HIV test orders	Order fulfillment	Proportion of participants sent a home HIV test	Benchmark ≥ 30%
Feasibility	Condom orders	Order fulfillment	Proportion of participants sent 'choice' condom package	Benchmark ≥ 30%
Feasibility	PrEP initiation	Clinical site data	Proportion of participants receiving a PrEP prescription	Benchmark ≥ 20%
Acceptability	Systems Usability Scale ^{126, 127}	Survey	10-item scale, good score is >71	Benchmark: Good score (≥ 71 out of 100)
Acceptability	Ratings for intervention components ⁷²	Survey	Likert acceptability rating for each intervention component (e.g. home HIV test)	Benchmark: Acceptable ratings (≥ 3 out of 5)
PRELIMINARY EFFICACY ASSESSMENT				
HIV testing	HIV testing ^{44,128}	Survey	Change in median number HIV tests	GEE model
Condom use	Condom use ^{44,128}	Survey	Change in proportion of participants reporting always using condoms for anal sex	GEE model
PrEP Use	PrEP use ¹²³⁻¹²⁵	Laboratory data	Number participants with protective levels of TDF-DP	Descriptive report
THEORETICAL ASSESSMENT				
Prevention cascade	PrEP cascade levels ¹²⁹	Survey and clinical site data	PrEP awareness, willingness, prescription, persistence in care, and medication adherence	Descriptive and logistic regression
Theoretical assessment	Unified Theory of Acceptance and Use of Technology (UTAUT2) ¹²¹	Survey	Validated items for performance expectancy, effort expectancy, social influence, hedonic motivation, and habit.	Descriptive and GEE model to estimate SEM parameters
PROCESS OUTCOMES				
Process	New HIV testers	Survey	Proportion changing from never to ever HIV test	Descriptive report
Process	New condom users	Survey	Proportion changing from none to some condom use	Descriptive report
Process	Visits to local health clinics	Survey	Proportion receiving HIV services at health departments	Descriptive report

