10.2 Power to Detect Effects in Primary Outcome

This is a feasibility pilot and therefore is not powered to detect significant differences relative to the baseline period. The use of a non-powered pilot design is called for by the MP3 mechanism. A sample of 200 individuals per intervention city was selected based on what was determined to be achievable given budget and time constraints. It is also anticipated that this number will provide estimates of key parameters with sufficient precision. For instance, the prevalence of our binary benchmarks (home HIV

test orders, PrEP initiation) would be estimable with the following 95% confidence intervals half-width at specified prevalences: $20\% \pm 4\%$; $30\% \pm 5\%$; $50\% \pm 5\%$.

Led by the study statistician, additional analyses will be conducted to assess (1) preliminary efficacy with endpoints measuring change from baseline to intervention periods in HIV testing, condom use, and PrEP use, (2) theoretical efficacy with endpoints in the PrEP cascade and UTAUT2 constructs, and (3) process outcomes with endpoints of new HIV testers, new condom users, and app use metrics. These assessment will leverage the pilot's interrupted time series design and inform future clinical trial design.

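### The PrEP feasibility benchmark is at least 15% in section 10.1 but at least 20% in the section 6.0 table, for the same primary measure

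*Combined protocol and SAP*

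**What the plan says.** Section 10.1 (Primary Outcome) gives the decision rule: "The intervention will be determined to be feasible if a minimum proportion of participants receive services for home HIV testing", with a 30% benchmark, "and PrEP prescription (benchmark $\geq 15" percent. On the origin of the thresholds it says: "Benchmark targets were determined based on modeling in other contexts that indicates minimum levels of service uptake to substantially influence an HIV epidemic". No modelled value is reported.

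The table in section 6.0 (Measures) lists PrEP initiation under primary outcomes, as a feasibility construct. Its definition is "Proportion of participants receiving a PrEP prescription" and its analysis entry is "Benchmark ≥ 20" percent.

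Section 10.2 names the binary benchmarks as home HIV test orders and PrEP initiation. It gives precision by way of example at 20%, 30% and 50% ("test orders, PrEP initiation) would be estimable with the following 95% confidence intervals half-width at specified prevalences"), and does not mention 15%.

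The table also has a third binary feasibility row with a 30% benchmark, condom orders ("Proportion of participants sent 'choice' condom package"). Sections 10.1 and 10.2 do not list it.

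**The concern.** Section 10.1 states that the primary analysis assesses feasibility and acceptability rather than efficacy, and does so against benchmarks. There is no primary hypothesis test behind them, so these thresholds are the primary decision rule. If uptake falls from 15% to just under 20%, section 10.1 says the PrEP criterion is met and the table says it is missed.

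The timing adds to the problem. No blinding is described, PrEP data are recorded on case report forms at clinic visits (section 7.4), and section 9.1 provides for weekly reports on laboratory results and progress through the intervention by site. Unless one value is fixed first, the choice between the two could be made by people who already know the uptake.

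**Working it through.** **1. Is it the same measure?**

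| Feature | Section 6.0 table | Section 10.1 |
|---|---|---|
| Role | Primary outcome, feasibility | Primary outcome, feasibility |
| Quantity | Proportion of participants receiving a PrEP prescription | Proportion of participants receiving a PrEP prescription |
| Limited to a subgroup, city or time point | No | No |
| PrEP benchmark | at least 20% | at least 15% |
| Home HIV test benchmark | at least 30% | at least 30% |
| Usability score | at least 71 | at least 71 |
| Component rating | at least 3 of 5 | at least 3 of 5 |

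The row label in section 6.0 speaks of initiation, but its definition column says prescription, as section 10.1 does. Every other benchmark given in both places agrees, so the PrEP figure is an isolated discrepancy and not part of a second scheme.

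**2. Does the plan's precision statement settle it?** The 95% half-width is 1.96 × √(p(1 − p)/n). With n = 400:

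- p = 20%: 1.96 × √(0.20 × 0.80/400) = 3.92 points (plan: 4)
- p = 30%: 1.96 × √(0.30 × 0.70/400) = 4.49 points (plan: 5)
- p = 50%: 1.96 × √(0.50 × 0.50/400) = 4.90 points (plan: 5)

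These reproduce the plan's figures when rounded up to whole points. With n = 200 (one city) the values are 5.54, 6.35 and 6.93, so the statement refers to the pooled sample. At 15% the half-width would be 1.96 × √(0.15 × 0.85/400) = 3.50 points. Using 20% as an example is compatible with the table but does not set a threshold.

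**3. Counts.** For n = 400 (section 3.2): 0.15 × 400 = 60 and 0.20 × 400 = 80. A result of 60 to 79 prescriptions (15.0% to 19.75%) passes section 10.1 and fails the table.

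**4. How likely is a result in that range?** The documents give no expected uptake, so true uptake p is an assumption, varied here. Let X be the number of prescriptions, X ~ Binomial(400, p). The chance that the two rules disagree is P(60 ≤ X ≤ 79) = P(X ≥ 60) − P(X ≥ 80).

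| Assumed true uptake | P(60 ≤ X ≤ 79) |
|---|---|
| 10% | 0.001 |
| 12.5% | 0.078 |
| 15% | 0.517 |
| 17.5% | 0.812 |
| 20% | 0.476 |
| 22% | 0.152 |
| 25% | 0.008 |

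The chance of meeting each benchmark:

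| Assumed true uptake | P(X ≥ 60), 15% rule | P(X ≥ 80), 20% rule |
|---|---|---|
| 15% | 0.521 | 0.004 |
| 17.5% | 0.919 | 0.107 |
| 20% | 0.996 | 0.520 |

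**5. Sensitivity to the denominator.** The Schema says "The sample for the pilot study will consist of approximately 400 MSM". At n = 360 the disputed range is 54 to 71, and at n = 440 it is 66 to 87. At 17.5% uptake the chance of disagreement is 0.788 and 0.832; at every uptake in the first table of step 4 it moves by less than 3 points from the value at 400. If the denominator were only 320, for example because it counts only men who reach the intervention period, the range would be 48 to 63 and the chance at 17.5% would be 0.761.

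**The case against.** The strongest reply concerns weight. This is an unpowered feasibility pilot (section 10.2). The benchmark is a descriptive threshold on a single-cohort proportion; no error rate, stopping rule or stated go/no-go rule depends on it. Aim 4 draws on preliminary information from the pilot and not on a pass/fail label. Observed uptake will be reportable either way, and a reader could apply either threshold. That is true, but section 10.1 does commit to declaring feasibility by these thresholds, and a pilot that is not powered still needs an unambiguous primary criterion. If one figure is a typing error, the documents do not show which.

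Three narrower points stand as limits on the finding:

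- Section 10.1 joins home testing and PrEP with an and. If home testing misses 30%, the PrEP conflict cannot change the feasibility verdict. The probabilities above describe the PrEP benchmark alone, so they are an upper bound on the chance that the overall verdict under section 10.1 is ambiguous.
- PrEP is offered only after month 3, and neither section says whether the denominator is all enrolled men or those who reach the intervention period. Step 5 shows that the effect is modest.
- The condom-order discrepancy is secondary. It alters the verdict only if all feasibility rows in the table are jointly required, which the table does not say.

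**Conclusion.** The contradiction is real and must be fixed. It affects the primary decision rule, and the documents contain nothing that identifies the intended value. A gap of 20 participants in 400 separates the two rules. The practical risk depends on true uptake, which the plan does not predict. It is largest between the two thresholds (81% at 17.5%), about one in two at either threshold, 8% at 12.5%, 15% at 22%, and negligible at 10% or 25%. These figures assume that all 400 enrolled men form the denominator and that prescriptions are independent with a common probability.

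**What to change.** - State one PrEP benchmark, identical in sections 6.0 and 10.1, before uptake data are viewed. Justify it by reporting the result from the modelling that section 10.1 cites.
- In section 10.2, give the precision at that value: 15% ± 3.5 points or 20% ± 3.9 points at n = 400.
- Name the denominator in both sections.
- State in section 10.1 whether condom orders count toward feasibility and, if so, whether they join the existing and-rule. If they do not count, move that row out of the primary outcomes block.
- If uptake has already been seen, document which value was set first and report the result against both.

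The edit is a few lines, but the choice is not neutral. At an assumed true uptake of 17.5%, the chance of meeting the benchmark is 92% under the 15% rule and 11% under the 20% rule. Making condom orders a required benchmark would add a further hurdle.
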